Appendix 4 Assessment of Health Scale

Health scale

Pre-flu health:

Please circle on the line below one number between 0 (worst possible health) and 10 (normal health for someone your age and your health condition) which best describes your pre-flu health.

Appendix 5 Management Criteria for Abnormal Liver Function Tests

Management Criteria for Abnormal Liver Function tests have been designed to ensure patient safety and evaluate liver event etiology (see Guidance for Industry Drug-Induced Liver Injury: Premarketing Clinical Evaluation, FDA: 2009).

1. Abnormal liver chemistry criteria:

The investigator or subinvestigator must review study patient laboratories to identify if any levels meet the following criteria:

- a. AST or $ALT > 5 \times ULN$
- b. AST or ALT $> 3 \times$ ULN and total bilirubin (TBL) $> 2 \times$ ULN or PT-INR > 1.5, if PT-INR is measured.
- c. AST or ALT > 3 × ULN with signs or symptoms compatible with hepatitis or hypersensitivity (eg, fatigue, nausea, vomiting, right upper quadrant pain or tenderness, jaundice, fever, rash, eosinophilia [> 5%])

2. Action to be taken by investigator:

If any abnormal liver chemistry criterion is met, the investigator or subinvestigator must do the following:

- Patients must be instructed to discontinue study medication immediately.
- Following the initial observed elevation, every effort should be made to have the patient return to the clinic within 72 hours to repeat liver function chemistries and for further hepatic evaluation.
- Every effort should be made to have the patients monitored 2 to 3 times per week until liver function chemistries (ALT, AST, ALP, TBL) resolve, stabilize, or return to within the normal range or to baseline levels.
- This event must be reported to the sponsor as soon as possible but no later than 72 hours of learning after its occurrence on the Liver Event Form.
- Consultation with a specialist such as a hepatologist is considered.
- Liver imaging (ie, ultrasound, magnetic resonance imaging [MRI], computerized tomography) is considered.
- For criteria b, the case must be reported as an SAE.

3. Follow-up examination:

If any of the abnormal liver chemistry criteria are met, the following assessments should be performed at the follow-up visit(s) and documented in the Liver Event Form:

- Clinical symptoms course
- Concomitant medications: OTC/herbal/dietary supplements (start and stop dates)
- Alcohol use

- Risk factors for nonalcoholic steatohepatitis (NASH), such as diabetes, obesity, and hypertriglyceridemia
- Autoimmune hepatitis/cholangitis
- Wilson's disease
- Laboratory assessments
 - Viral hepatitis serology
 - o Hepatitis A IgM antibody
 - Hepatitis B surface antigen (HBs antigen) and hepatitis B core antibody (HBc antibody)
 - o Hepatitis C RNA
 - Hepatitis E IgA antibody
 - o Cytomegalovirus IgM antibody
 - o Epstein-Barr viral capsid antigen IgM antibody
 - For patients with TBL of > 1. 5 x ULN, conjugated bilirubin should be measured
 - Complete blood count with differential to assess for eosinophilia

4. Restarting Study Medication Criteria

Patients that meet the abnormal liver chemistry criteria may restart the administration of the study drug, but only if they do not meet the "Drug Discontinuation Criteria Due to Abnormal Liver Chemistry Tests".

Patients with ALT > $5 \times ULN$ to $\le 8 \times ULN$ elevations for < 2 weeks may restart the administration of the study drug at the discretion of the investigator and sponsor if both of the following conditions are met:

- Subsequent liver function chemistries are lower or unchanged
- No signs or symptoms are consistent with hepatitis or hypersensitivity (eg, fatigue, nausea, vomiting, right upper quadrant pain or tenderness, jaundice, fever, rash or eosinophilia [>5%])

All patients that have met abnormal liver chemistry criteria must still be monitored 2 to 3 times per week until liver function chemistries (ALT, AST, alkaline phosphatase, and total bilirubin) resolve, stabilize, or return to within the normal range or to baseline levels.

[figure not shown]
5. Drug Discontinuation Criteria Due to Abnormal Liver Chemistry Tests

Patients must be discontinued from the study as described below:

a. AST or ALT > 8 × ULN, confirmed by follow-up testing (ie, initial abnormality is confirmed on subsequent testing), regardless of medical history or physical examination findings

- AST or ALT > 5 × ULN, with elevations for more than 2 weeks or development of concomitant signs or symptoms consistent with hepatitis or hypersensitivity (eg, fatigue, nausea, vomiting, right upper quadrant pain or tenderness, jaundice, fever, rash or eosinophilia [>5%])
- c. AST or ALT > 3 × ULN and total bilirubin > 2 × ULN or PT-INR > 1. 5, if PT-INR measured, confirmed by follow-up testing (ie, initial abnormality is confirmed on subsequent testing), regardless of medical history or physical examination findings

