7.8 Withdrawal of Patients from the Study or Study Treatment

The investigator will make every reasonable attempt to complete the study for each enrolled patient. A patient may withdraw for any reason. The investigator will advise the sponsor about the withdrawal of any patient by the IWRS.

The investigator will withdraw a patient from the study or the study drug treatment for any of the following reasons:

- A serious or intolerable AE occurs and the investigator considers that the patient should be withdrawn because of the AE
- The patient requests to be withdrawn from the study
- The patient is lost to follow-up
- The investigator determines that the patient should be withdrawn because of other reasons
- The investigator determines that the patient should be withdrawn based on the management and discontinuation criteria for abnormal liver function tests

In the event of a patient's withdrawal, the investigator will promptly notify the sponsor and will make every effort to complete the end-of-study (or ET) assessments. All patients withdrawn due to AEs will be followed until resolution of any AEs, until the unresolved AEs are judged by the investigator to have stabilized, or the patient is lost to follow-up. The date of completion (if completed the follow-up period), date of discontinuation (if discontinued before Day 22), period of discontinuation, and reason for discontinuation will be entered in the eCRF.

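### Appendix 5 item 4 ties its restart conditions to ALT alone, so a symptom-free patient with AST > 5 to 8 × ULN and ALT ≤ 5 × ULN may restart while AST is still rising

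*Protocol*

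**What the plan says.** Appendix 5 of the protocol handles abnormal liver tests in steps. Item 1 lists three triggers (1a to 1c), and item 2 requires an immediate stop of study medication when any is met. Item 4 governs restart and item 5 lists the criteria for permanent discontinuation.

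Item 4 has two parts. The first is general: "Patients that meet the abnormal liver chemistry criteria may restart the administration of the study drug, but only if they do not meet the" item 5 criteria. The second concerns ALT above 5 and up to 8 × ULN. Patients with such "elevations for < 2 weeks may restart the administration of the study drug at the discretion of the investigator and sponsor", provided two conditions hold. One is "Subsequent liver function chemistries are lower or unchanged"; the other is the absence of signs or symptoms of hepatitis or hypersensitivity. AST is not named in this second part.

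Item 5 names both enzymes throughout. Its middle criterion, 5b, reads "AST or ALT > 5 × ULN, with elevations for more than 2 weeks or development of concomitant signs or symptoms" of hepatitis or hypersensitivity. No item 5 criterion refers to values that are still rising.

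**The concern.** The two enzymes are treated alike when the drug is stopped and when it is permanently discontinued, but not when it is restarted. Section 7.6.5.8 also refers to AST or ALT throughout, and the protocol gives no reason for a different rule at restart. Read literally, the trend condition and the joint decision of investigator and sponsor fall away when AST is the enzyme above 5 × ULN and ALT is not. At stake is the safety of a re-exposure decision. In the oseltamivir arm the capsules are active, and Section 1.3.1.2 lists serious hepatic disorders among that drug's rare reactions.

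**Working it through.** This is a check of rule logic; there is no planned figure to reproduce.

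**Step 1. The rules side by side (Appendix 5).**

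| Item | Enzyme | Level (× ULN) | Further requirement |
|---|---|---|---|
| 1a stop | AST or ALT | > 5 | none |
| 1b stop | AST or ALT | > 3 | bilirubin > 2 × ULN or PT-INR > 1.5 |
| 1c stop | AST or ALT | > 3 | signs or symptoms |
| 4 conditional restart | ALT only | > 5 to ≤ 8, for < 2 weeks | not rising; no signs or symptoms; investigator and sponsor discretion |
| 5a discontinue | AST or ALT | > 8 | confirmed |
| 5b discontinue | AST or ALT | > 5 | > 2 weeks, or signs or symptoms |
| 5c discontinue | AST or ALT | > 3 | bilirubin > 2 × ULN or PT-INR > 1.5, confirmed |

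**Step 2. Two mirror-image patients.** Both have no symptoms, less than 2 weeks of elevation, bilirubin and PT-INR not raised, and rising values.

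- ALT 6.5, AST 4: stopped under 1a. 5a, 5b and 5c are not met. The item 4 conditions apply, and the rising value bars restart.
- AST 6.5, ALT 4: stopped under 1a. 5a, 5b and 5c are not met. The item 4 conditions do not apply, so the general permission governs and restart is allowed.

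If the AST patient has symptoms or more than 2 weeks of elevation, 5b bars restart. What is lost is therefore the trend condition and the discretion step, not the symptom rule.

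**Step 3. How many combinations are affected.** Keep the same setting and require the higher enzyme to lie in > 5 to 8. With bands ≤ 3, > 3 to 5 and > 5 to 8 for each enzyme, there are 3 + 3 − 1 = 5 combinations. Item 4 covers the 3 with ALT > 5 to 8. It misses 2: AST > 5 to 8 with ALT ≤ 3, and with ALT > 3 to 5.

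**Step 4. What can be restarted.** S-033188 is given once on Day 1 (Section 3.1). Only the 10 capsules (Section 5.6), taken twice daily, can be resumed. Chemistry is scheduled on Days 1, 5, 15 and 22 (Section 7.6.4.1). Laboratory turnaround is not stated, so the day of action is an assumption. Doses missed while off drug are assumed not to be added at the end.

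Capsules left at restart = max(0, 10 − taken before the stop − 2 × days off drug). Values in brackets are for patients who took only one capsule on Day 1 (Table 5-1 footnote).

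| Stop at end of | Taken | Restart after 24 h | 48 h | 72 h |
|---|---|---|---|---|
| Day 2 | 4 (3) | 4 (5) | 2 (3) | 0 (1) |
| Day 3 | 6 (5) | 2 (3) | 0 (1) | 0 (0) |
| Day 5 | 10 (9) | 0 (0) | 0 (0) | 0 (0) |

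Samples from Days 15 and 22 leave none. The range for a Day 1 sample acted on at the end of Day 2 or 3 is thus 0 to 5. It is not a strict bound: action already at the end of Day 1 would leave 10 − 2 − 2 = 6 (7) capsules at a 24-hour restart. If missed doses were added at the end, a Day 2 stop would leave 10 − 4 = 6 (7).

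**The case against.** **The ALT paragraph may be the only restart route above 5 × ULN.** AST-only cases would then stay stopped. That reading is possible, but the opening sentence of item 4 is a general permission limited only by item 5. On the narrow reading, AST-only patients have no restart rule at all. The same edit settles the matter either way.

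**Other safeguards remain.** This stands. Item 2 asks that every effort be made to have the patient "return to the clinic within 72 hours to repeat liver function chemistries and for further hepatic evaluation", and requires a Liver Event Form to the sponsor within 72 hours. Monitoring 2 to 3 times per week is set out in items 2 and 4. Item 3 calls for the "Clinical symptoms course" to be documented. Section 7.8 allows withdrawal where "The investigator determines that the patient should be withdrawn because of other reasons". Item 4 permits a restart and does not require one. But none of these is a condition for restarting.

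**The group is very small.** This also stands. The realistic trigger is a Day 1 or unscheduled sample, and on Day 1 patients have fever and influenza symptoms by the entry criteria. Fever and fatigue are among the examples listed in 5b. If 5b is taken to include influenza symptoms already present at entry, it bars restart and the gap closes for those patients. The text does not settle this.

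**A stronger reading is tempting for 1c.** That trigger is "AST or ALT > 3 × ULN with signs or symptoms compatible with hepatitis or hypersensitivity". At > 3 to 5 × ULN with bilirubin and PT-INR not raised, no item 5 criterion is met and item 4 sets no trend or symptom condition. A reader might call this a second error. The document does not support that. Item 5 is graded, with symptoms barring restart only above 5 × ULN, so a lighter rule below that level is consistent with it. Influenza itself can supply the fever or fatigue that meets 1c, so a strict symptom condition would block most restarts. This is a clinical trade-off for the medical team to confirm.

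**Conclusion.** The point holds for AST. Item 4 omits AST from a conditional rule whose stop and discontinuation counterparts cover both enzymes. As a result, a symptom-free patient with AST > 5 to 8 × ULN and ALT ≤ 5 × ULN may restart while AST rises and without the discretion step. It is a minor wording defect in a safety rule. It bears on a few oseltamivir or placebo capsules in rare patients, and on no part of the statistical analysis.

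The conclusion rests on reading the first sentence of item 4 as a general permission, on bilirubin and PT-INR not being raised (or PT-INR not measured), and on the unreadable figure between items 4 and 5 adding no restart condition. The capsule counts rest on the assumed day of action and on missed doses not being made up.

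**What to change.** In Appendix 5 item 4, change the group to which the restart conditions apply from ALT > 5 × ULN to ≤ 8 × ULN to **AST or ALT > 5 × ULN to ≤ 8 × ULN**. The two conditions and the discretion step then apply to both enzymes, matching items 1 and 5.

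The cost is one phrase in an amendment, with no extra tests or visits. The downside is that a few patients with a rising AST may be kept off their remaining capsules. In the same round the medical team could confirm whether the absence of restart conditions after a 1c stop at > 3 to 5 × ULN is intended; the point above does not depend on the answer.
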